**PARTNERS HUMAN RESEARCH COMMITTEE
PROTOCOL SUMMARY**

Answer all questions accurately and completely in order to provide the PHRC with the relevant information to assess the risk-benefit ratio for the study. Do not leave sections blank.

PRINCIPAL/OVERALL INVESTIGATOR

[name]

PROTOCOL TITLE

Treatment of Field Cancerization for Reduction in Tumor Burden – A Prospective Study

NCT NUMBER

NCT02150863

FUNDING

Wellman Center for Photomedicine

VERSION DATE

December 28, 2016

SPECIFIC AIMS

Concisely state the objectives of the study and the hypothesis being tested.

This project aims to treat field cancerization in a manner that will reduce the tumor burden in patients with significant photodamage

1. To demonstrate that we can reduce the non melanoma skin tumor burden over time by treating the entire field of actinic keratoses and atypical keratinocytes.
2. To compare the efficacy and side effects of ablative CO2 laser resurfacing vs. ablative CO2 laser resurfacing plus post treatment suction blister epidermal grafts vs. control (no intervention).
3. To demonstrate a reduction in the number of actinic keratoses over time
4. To demonstrate an improvement in clinical appearance of the treatment area
5. To demonstrate a reduction in the degree of P53 mutations seen with histopathology
6. To demonstrate that subjects tolerate the treatment with few side effects
7. To demonstrate increased telomere length in treated areas

BACKGROUND AND SIGNIFICANCE

Provide a brief paragraph summarizing prior experience important for understanding the proposed study and procedures.

Field cancerization is a risk for any individual with excessive and prolonged sun exposure, immunosuppression, or exposure to radiation or carcinogens. We are very good at treating the skin cancer but if we leave behind the atypical field of keratinocytes it is only a matter of time

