until the next skin cancer needs to be excised. The current treatment regimens for treating AKs and SCCs involve frequent office visits with extensive cryotherapy, numerous biopsies and excisions. We often use topical medications to treat field cancerization, such as 5-fluorouracil or imiquimod. These treatments are often ineffective and need to be repeated frequently. The need for multiple treatments may be related to compliance. Often people cannot tolerate these treatment regimens. Thus there is the need for an optimized treatment regimen to improve clearing the field of atypia and precancerous lesions. This would cut down on cost, risks of surgical procedures, and patient discomfort.

We want to evaluate of effectiveness of ablative carbon dioxide (CO2) laser used to precisely remove the epidermis of an entire field, thus removing all the typical keratinocytes and basal stem cells that have been mutated. After the CO2 treatment a portion of the area treated would then be covered with autologous epidermal skin grafts from a non-exposed area (buttocks or thigh). We hypothesize that the epidermal skin grafts would not only improve/hasten the wound healing process after CO2 but it would also provide the field with stem cells that have yet to receive damaging radiation.

Ablative CO2 laser was first used by surgeons to cut and vaporize tissue. It then became a popular device with both surgeons and dermatologists for treatment of deep facial rhytides. More recently these lasers have been used to treat significantly photodamaged skin and actinic keratoses. The studies showing varying rates of reduced AK counts over short periods of time. The longest follow up being 2 years.

Suction blister autologous epidermal grafting is a simple procedure being used most commonly for vitiligo, but also wound healing and scarring. There are several IRB approved protocols at MGH already using this technique (PI: [name], MPH).

RESEARCH DESIGN AND METHODS

Briefly describe study design and anticipated enrollment, i.e., number of subjects to be enrolled by researchers study-wide and by Partners researchers. Provide a brief summary of the eligibility criteria (for example, age range, gender, medical condition). Include any local site restrictions, for example, "Enrollment at Partners will be limited to adults although the sponsor's protocol is open to both children and adults."

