The proposed pilot study is a 3 year prospective, randomized, controlled comparison of a single treatment with carbon dioxide laser resurfacing vs. carbon dioxide resurfacing plus autologous epidermal skin graft from a non sun exposed site vs. control. Thirty subjects will receive treatment with each of the modalities on randomly-assigned portions of the treatment area. The primary measures of efficacy are (a) count of the number of actinic keratosis and non melanoma skin cancers, (b) blinded evaluation of severity from standard digital photographs taken before and after the treatments, and (c) change in histology before and after treatment: seen by grading and change of p53 immunostaining. Other study endpoints include time point to the next skin cancer is found in the treatment area, overall clinical appearance, change in mutant P53 of skin samples, and telomere length variability.

Safety measures include (a) pain, (b) scarring, (c) wound healing, (d) and infection

Subjects will be recruited through advertisements posted within the hospital(s), outpatient dermatology clinics and partners electronic mail.

Inclusion criteria

1. Subjects with ages between 18 and 85 years, male or female.
2. Subjects with at least 4 clinically diagnosed AKs per treatment site (up to 200 sq cm), excluding the face.
3. Subjects with history of at least 1 skin cancer within the past year
4. Willingness to participate in the study
5. Informed consent agreement signed by the subject
6. Willingness to follow the treatment schedule and post treatment care requirements
7. Willingness to not use topical or systemic (oral) TREATMENT medications including imiquimod, 5 Fluorouracil, photodynamic therapy, during the treatment period.
8. Has not had treatment for AKs in the treatment area for 4 weeks prior to enrollment

Exclusion criteria

1. Subjects with active skin cancer in the treatment area. Once the non-melanoma skin cancer has been treated, the subject can be immediately enrolled.
2. Infection of the area to be treated
3. An open wound in the area to be treated
4. Presence of suntan in the area to be treated, or active tanning during the study
5. Subjects who have taken medication known to induce photosensitivity in the previous 3 months
6. The patient has any contraindication to use of the CO2 laser
7. Subject is unable to comply with treatment, home care or follow-up visits
8. Subject is pregnant or breast feeding

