Visit	Informed consent	Urine preg test	TX	Photo	# NMSC prior	AK/NMSC count	Biopsy	Overall Appearance scale	AE	Pain scale (VAS)	Patient side effect report	Inv wound assess
Screen	X											
Baseline/TX (Day 0)		X	X	X	X	X	X	X	X			
Day 3				X				X	X	X	X	X
Day 7				X				X	X	X	X	X
Week 4				X		X		X	X	X	X	X
3 month				X		X	X	X	X			X
6 month				X		X		X	X			
1 year				X		X		X	X			
1.5 – 2.5 year visits				X		X			X			
3 year				X		X	X	X	X			

Baseline/Treatment Visit 1(Day 0)

- Baseline and treatment can occur on separate days if necessary. These visits will occur within 2 weeks of each other if done separately**

Part I– Baseline Evaluations (lasting 1 hour).

Part II- Treatment (lasting 2.5 hours)

Part I– Baseline Evaluations (lasting 1 hour).

The investigator will determine the treatment area

- I. AK count within the treatment area**
- II. Confirm no clinically evident NMSC within the treatment area**
- III. Obtain history of number of skin cancers and locations. History will be taken orally from patient but will also review the medical records.**
- IV. Tracings of the treatment area and control site as needed to document**

V. Shave biopsy technique will be used to harvest epidermal biopsies for histologic assessment. 6 scouting biopsies will be done in the treatment area for histologic evaluation and immunostaining

VI. Baseline pre-treatment Photography of treatment area and control site

Shave biopsy for histology

Area will be prepped with alcohol swab, injected with Lidocaine 1% with or without epinephrine. Shave biopsy will be performed with a dermablade. Tissue samples will be taken to the lab and processed for immunostaining of p53 and PCR to determine telomere length. A portion will be frozen and backed for PCR analysis at the end of the study.

Part II- Treatment (lasting 2.5 hours)

- I) Urine pregnancy test for female not yet in menopause
- II) Subject will receive laser treatment to the treatment area. Topical anesthesia will be applied for 1 hour prior to the laser treatment.
- III) Epidermal suction blister graft harvest from donor site and application on randomized treatment area
- IV) Adverse event evaluation
- V) Patient assessments: pain

Procedures in more detail

Laser treatment

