The laser used is the Ultrapulse CO2 Laser (Lumenis). Patients will be treated according to the standard of care. The settings used for the CO2 laser will be commonly used settings that will ablate down to the bottom layer of the epidermis (8 – 20 J/cm²). Any remaining epidermis will be removed with saline soaked gauze. The papillary dermis has a characteristic glistening appearance and this will also be used as a treatment endpoint. If the papillary dermis is seen, the treatment in that area will be considered completed.

Participants or caregivers will be instructed to do saline soaked gauze soaks three times daily and apply Vaseline™ or Aquaphor™ onto the treated areas for up to 7 days post op as needed. Wound care instructions will be given to the patient, and a Day 3 follow-up visit will be scheduled.

Epidermal Blistering and Micrograft Preparation

A suction device will be applied to area of skin approximately 5.0 cm in diameter. This will be left in place approximately 30-40 minutes and may cause mild discomfort because of the suction. After the microblisters have been raised, the blister roofs (a superficial epidermal sample) with an average thickness of 200 microns and size of 1.75 mm in diameter will be removed and transferred to a sterile Tegaderm wound dressing that will be applied to the recipient site. The superficial donor wound will then covered with sterile Tegaderm or Duoderm.

Post- Procedure follow up Visits (Day 3, Day 7) (lasting 30 minutes)

- I) Photography

- II) Exam of the treatment area: wound check; evidence of scarring, evidence of infection; evidence of healing
- III) Adverse event evaluation
- IV) Investigator assessments: wound assessment, overall clinical appearance
- V) Patient assessments: pain scale and side effects

Follow-up Visits(Week 4) (lasting 30 minutes)

- I) Photography
- II) Exam of the treatment area: AK count, evaluate for clinically appearing NMSC present; evidence of scarring, evidence of infection; evidence of healing. Also will get history from patient: visits to dermatologist? and treatments rendered?.
- III) Adverse event evaluation
- IV) Investigator assessments: wound assessment, overall clinical appearance
- V) Patient assessments: Pain scale and side effects

Follow-up Visits

(Month 3) (lasting 1.5 hours)

- I) Photography

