- II) Exam of the treatment area: AK count, evaluate for clinically appearing NMSC present; evidence of scarring, evidence of infection; evidence of healing . Also will get history from patient: visits to dermatologist? and treatments rendered? Will also review medical records to confirm the history.
- III) 6 scouting epidermal biopsies, using shave biopsy technique (from the treatment area) for histology and immunostaining. Will also bank a portion for PCR at the end of the study.
- IV) Adverse event evaluation
- V) Investigator assessments: wound assessment, overall clinical appearance

Follow-up Visits(6 months, 1 year, 1.5 year, 2 year, 2.5 year) (lasting 30 minutes each)

- I) Photography
- II) Exam of the treatment area: AK count, evaluate for clinically appearing NMSC present; evidence of scarring, evidence of infection; evidence of healing . Also will get history from patient: visits to dermatologist? and treatments rendered? Will also review medical records to confirm the history.
- III) Adverse event evaluation
- IV) Investigator assessments: overall clinical appearance

End of Study visit (3 year) (lasting 1.5 hours)

Patients will exit the study after 3 years

- II) Photography
- III) Exam of the treatment area: AK count, evaluate for clinically appearing NMSC present; evidence of scarring, evidence of infection; evidence of healing . Also will get history from patient: visits to dermatologist? and treatments rendered? Will also review medical records to confirm the history

- IV) **6 scouting epidermal biopsies, using shave biopsy technique (from the treatment area) for histology and immunostaining. Will also bank a portion for PCR at the end of the study.
- V) Adverse event evaluation
- VI) Investigator assessments: overall clinical appearance

** During the course of the study, the subjects will have a total of 18 scouting epidermal biopsies using the shave biopsy technique

Evaluation of Safety and Efficacy

Assessed by investigators (non-blinded) and by blinded evaluators (clinical photographs), periodically for 3 years after a single treatment session.

Reported by the Patients

Specific form is attached.

I. Side effects reported by the patient:

To assess major and minor side-effects, patients will be asked for each treatment site to fill in the following sentence for each test site: **“The side effects I experienced after the treatment were:”** E.G.

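### Aim 2 compares the side effects of laser with laser plus graft, but no graded assessment is clearly assigned to the graft donor wound

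*Protocol*

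**What the plan says.** Specific Aims, item 2, begins "To compare the efficacy and side effects of ablative CO2 laser resurfacing" and sets this against laser plus suction blister grafts and against an untreated control. Research Design and Methods states that "Thirty subjects will receive treatment with each of the modalities on randomly-assigned portions of the treatment area", and that "Safety measures include (a) pain, (b) scarring, (c) wound healing, (d) and infection".

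The Background section places the graft source on the buttocks or thigh. Part II of the Day 0 visit treats that source and the treated field as two different places: "Epidermal suction blister graft harvest from donor site and application on randomized treatment area". The section on blistering and micrograft preparation gives the only later instruction about the source site: "The superficial donor wound will then covered with sterile Tegaderm or Duoderm".

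Follow-up is described by treatment area. Day 3 and Day 7, item II, read "Exam of the treatment area: wound check; evidence of scarring, evidence of infection; evidence of healing". Week 4, Month 3 and the later visits read "Exam of the treatment area: AK count, evaluate for clinically appearing NMSC present; evidence of scarring, evidence of infection; evidence of healing". The patient side-effect form (Table I) is described as completed for each treatment or test site. The visual analog scale (VAS) for pain names no site and asks about pain from the disease. The investigator wound assessment (Table 2) names no site. The protocol says that specific forms are attached; they are not shown.

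**The concern.** The donor wound is a harm that only one of the compared modalities can cause. Leaving it out of the graded assessments does not affect the modalities equally: it removes a cost from CO2 plus graft and nothing from CO2 alone or control. Any resulting distortion favours grafting.

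The named safety measures are pain, scarring, wound healing and infection, and each of them can arise at a harvest site. If the exam and patient-form wording is followed literally, effects at the laser sites are asked about item by item and graded, while effects at the donor site are recorded only if the subject volunteers them or the assessor chooses to look. The two sources of harm are then not ascertained alike. An analysis plan cannot repair this later, because it cannot recover grades that were never collected.

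**Working it through.** The protocol gives no figure on this point to reproduce. The check is a reading of each assessment for its site, followed by simple counts.

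**Where the donor site appears.** It is mentioned as the origin of the skin (Background), in the harvest step (Day 0, Part II) and in the dressing instruction. It is not named in any scheduled exam, graded table, scale or endpoint.

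**Scope of each assessment as written**

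| Assessment | Visits | Stated site |
|---|---|---|
| Exam for scarring, infection, healing | All 10 follow-up visits, Day 3 to Year 3 | Treatment area |
| Patient side-effect form (Table I) | Day 3, Day 7, Week 4 | Each treatment or test site |
| Pain VAS | After treatment, Day 3, Day 7, Week 4 | None; worded for the disease |
| Investigator wound assessment (Table 2) | Day 3, Day 7, Week 4, Month 3 | None |
| Overall appearance scale | Per visit schedule | CO2, CO2 plus graft, control |
| Adverse events | Day 0 and every follow-up visit | Not limited to a site |

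Table 2 is the only itemised graded side-effect instrument whose wording could reach the donor wound without strain.

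**How far Table 2 would go.** The risk section lists 11 suction-blister risks, without giving severity or separating donor from recipient site: pain, swelling, redness, crusting, tenderness or burning, itching, small scar, bruising, bleeding, discoloration and infection.

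- On Table 2 as shown: swelling, redness, crusting, scarring, hyper- or hypopigmentation, infection = 6.
- Not on Table 2: 11 − 6 = 5. Itching and bleeding are on the patient form only. Pain and tenderness or burning fall under the VAS only. Bruising is on no scale.

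The row numbering of both tables has gaps, so an item may have been lost when the text was extracted.

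**Number of assessments affected by a correction** (30 subjects, all planned to receive every modality)

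- Exams at Day 3, Day 7, Week 4, Month 3: 4 × 30 = 120.
- Patient forms at Day 3, Day 7, Week 4: 3 × 30 = 90.
- Wound assessments at Day 3, Day 7, Week 4, Month 3: 4 × 30 = 120.

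These counts show the reach of the change. They do not measure bias.

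**The case against.** The strongest reply is that the matter may be settled on forms that cannot be seen. The patient, VAS and investigator forms are all said to be attached, and any of them could carry a donor-site line. This stands as a limit on confidence. It does not remove the point, because the exam text would still need to match such a form.

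Second, the investigator wound assessment is listed separately from the exam of the treatment area and has no site limit. Since the protocol itself calls the harvest site a wound, an assessor could well include it. That is a fair reading, but it leaves the scope to each assessor, and Table 2 as shown covers only part of the listed risks.

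Third, adverse events and side effects from treatment are collected at every visit without a site restriction, and harvest belongs to the treatment session. So donor harms are not wholly uncollected. What is lacking is solicited, itemised grading of the kind used for the treatment sites.

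Fourth, the VAS wording about disease looks like an unfilled template field and is just as awkward for laser pain. This is true, and that wording alone is weak evidence of a donor-site gap.

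Fifth, the donor wound has no counterpart in the CO2-alone portion, so grading it yields no paired contrast, and this is a pilot. That also stands and restricts the remedy to descriptive reporting. It does not justify leaving a graft-specific harm out of the graft's side-effect profile.

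**Conclusion.** The concern holds as a minor point with medium confidence. As written, the protocol clearly assigns no graded assessment to the donor wound, while Aim 2 rests on a comparison of side effects in which that wound belongs to one modality only. The direction of any bias is predictable, towards making grafting look better tolerated. Its size cannot be estimated, because the protocol gives no rate or severity for donor-site effects.

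The conclusion assumes that the attached forms do not already provide for the donor site and that assessors follow the stated exam scope. It does not claim that donor harms go unrecorded. The superficial nature of the wound and the general adverse-event collection keep the severity low.

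**What to change.** At Day 3, Day 7, Week 4 and Month 3, widen the exam to the treatment area and the graft donor site. State that the patient side-effect form (Day 3, Day 7, Week 4) and the investigator wound assessment (the same visits and Month 3) include the donor site, with a donor-site column on each if the attached forms lack one. Report donor-site findings descriptively as part of the CO2-plus-graft side-effect profile.

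A separate donor-site pain score at the existing VAS time points is optional and descriptive. Bruising, which is on no scale as shown, would need its own line if it is to be graded. Donor exams under this change would end at Month 3, while the treatment-area exam for scarring runs to Year 3, so late donor scars would still depend on adverse-event reporting.

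The cost is one form column and a minute or two at visits already scheduled, with no new visit, staff or procedure. The reported profile of CO2 plus graft may look less favourable. The donor-site grades will describe the added burden of grafting and cannot serve as a paired comparison with CO2 alone.

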Table I. **N/A:** Did not have this side effect / **1:** Mild / **2:** Moderate / **3:** Severe

A. Blistering	N/A	1	2	3
B. Scarring	N/A	1	2	3
1. Swelling	N/A	1	2	3
2. Redness	N/A	1	2	3
3. Scabs (crusting)	N/A	1	2	3
4. Weeping skin (pustulation)	N/A	1	2	3
5. Scaling or flaking skin (exfoliation)	N/A	1	2	3
6. Itchy skin	N/A	1	2	3
7. Erosion (ulceration)	N/A	1	2	3
8. Tanning	N/A	1	2	3
9. Lightening of the skin	N/A	1	2	3
11. Wheals	N/A	1	2	3
12. Bleeding	N/A	1	2	3
13. Folliculitis/ Acne	N/A	1	2	3
14. Oozing	N/A	1	2	3
15. Change in sensitivity/numbness	N/A	1	2	3

[figure not shown]
I. Pain assessment - Visual Analog Scale (VAS).

The VAS will be completed by study subject immediately after the treatment, and at each procedure follow up visit (Day 3, Day 7, week 4)

Pain is any of the following: sensation of tingling, stinging, prickling, or burning feeling, heat under the skin, tenderness, mild, moderate or severe pain).

Specific VAS form is attached

Patients will be asked to circle the number below that most closely corresponds to pain associated with their DISEASE.

Reported by the Investigators and Blinded-evaluators

Reported by the Investigator

Specific form is attached.

Investigator's Wound Assessment

Table 2. N/A: Did not have this side effect / 1: Mild / 2: Moderate / 3: Severe

A. Blistering	N/A	1	2	3
B. Scarring	N/A	1	2	3
1. Swelling	N/A	1	2	3
2. Redness	N/A	1	2	3
3. Crusting	N/A	1	2	3
4. Pustulation	N/A	1	2	3
5. Scaling or flaking skin (exfoliation)	N/A	1	2	3
6. Erosion (ulceration)	N/A	1	2	3
7. Hyperpigmentation	N/A	1	2	3
9. Hypopigmentation	N/A	1	2	3
10. Urticaria	N/A	1	2	3
11. Infection	N/A	1	2	3
12. Folliculitis/ Acne	N/A	1	2	3
14. Oozing	N/A	1	2	3

--	--

Overall Appearance Scale (blinded MD to complete with photos)

- Physicians will consider both cosmetic appearance but also the degree of photodamage and clinical atypia.

	Co2 treatment site	Co2 + epidermal graft Treatment site	Control site
Excellent	 5	 5	
Good	 4	 4	
Satisfactory	 3	 3	
Poor	 2	 2	
Unacceptable	 1	 1	

End points:

- AK count
- NMSC count
- change in overall clinical appearance
- time to healing

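### The schedule and the visit text disagree on rating overall appearance at 1.5, 2 and 2.5 years, and the protocol does not say whether the blinded or the unblinded rating is the endpoint

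*Protocol*

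**What the plan says.** The visit schedule has a column headed "Overall Appearance scale". It is marked at Day 0, Day 3, Day 7, Week 4, 3 months, 6 months, 1 year and 3 years. The row "1.5 – 2.5 year visits" has marks for photographs, the lesion count and adverse events, and none for appearance. The schedule names no rater.

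The visit text has a single procedure list headed "Follow-up Visits(6 months, 1 year, 1.5 year, 2 year, 2.5 year", and that list includes "Investigator assessments: overall clinical appearance". The lists for Day 3, Day 7, Week 4, Month 3 and Year 3 also place overall clinical appearance among the investigator's assessments.

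On who rates, the section Evaluation of Safety and Efficacy says: "Assessed by investigators (non-blinded) and by blinded evaluators (clinical photographs), periodically for 3 years after a single treatment session". It does not assign outcomes to one group or the other. The rating form is headed "Overall Appearance Scale (blinded MD to complete with photos" and has one column for each of the CO2 site, the CO2 plus graft site and the control site. Data and Safety Monitoring adds that overall efficacy assessments are done by blinded investigators.

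The End points list includes "change in overall clinical appearance". Aim 4 is an improvement in the clinical appearance of the treatment area. Research Design and Methods names overall clinical appearance among the other endpoints, apart from primary measure (b), which is a blinded photographic evaluation of severity.

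**The concern.** Two parts of the current text give different instructions. Staff working from the schedule would record no appearance rating between 1 and 3 years, and staff working from the visit text would record three. This matters for a study that sets out to show an effect over time.

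The rater is also unsettled. Appearance is a subjective five-level judgement, the comparator is an untreated site, and the protocol itself expects the control sites to improve less than the treated ones. An unblinded rater with that expectation can favour the treated sites. A blinded photograph reading is meant to guard against this, but only if that reading is the one analysed. The protocol does not say that it is.

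**Working it through.** The protocol states no figure to reproduce. The check compares the schedule with the visit text and counts visits.

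**Post-treatment visits.** Day 3, Day 7, Week 4, 3 months, 6 months, 1 year, 1.5 years, 2 years, 2.5 years and 3 years make 10. This agrees with the 10 study visits after the baseline/treatment visit given in the description of study procedures.

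| Visit | Photographs (schedule and text) | Appearance in schedule | Appearance in visit text |
|---|---|---|---|
| Day 0 | yes | yes | not listed |
| Day 3, Day 7, Week 4 | yes | yes | yes, investigator |
| 3 months | yes | yes | yes, investigator |
| 6 months, 1 year | yes | yes | yes, investigator |
| 1.5, 2, 2.5 years | yes | **no** | **yes, investigator** |
| 3 years | yes | yes | yes, investigator |

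**Rated post-treatment visits.**
- Schedule: 3 + 1 + 2 + 0 + 1 = 7 of 10.
- Visit text: 3 + 1 + 2 + 3 + 1 = 10 of 10.
- Difference: 10 − 7 = 3 visits.

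**Size of the difference.** With the 30 planned subjects and no dropout, 3 × 30 = 90 subject-visits. Each subject has three sites, so this is up to 90 × 3 = 270 site ratings.

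**Is the blank cell an extraction fault?** Unlikely. The marks for photographs, lesion count and adverse events in that row fall in the same columns as in the 6-month and 1-year rows. The row has exactly one mark fewer, the one for appearance.

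**Who rates.** The visit text gives appearance to the investigator at all 10 post-treatment visits, and Evaluation of Safety and Efficacy calls investigators non-blinded. The form gives the only appearance scale described to a blinded physician with photographs, and Data and Safety Monitoring points the same way. No section states that there are two appearance ratings, or which one supplies the endpoint. This question therefore concerns all 10 visits, not only the three in dispute.

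**Day 0.** The schedule marks the scale at Day 0, but the Day 0 text lists only photography of the treatment area and control site. A change score needs this baseline rating, so the text should list it.

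**The case against.** The strongest reply is that the protocol intends two parallel assessments, one by the unblinded investigator in clinic and one by a blinded reader from photographs. Evaluation of Safety and Efficacy names both groups, and the visit text attaches no scale to the investigator's item. The form heading and Data and Safety Monitoring then point to the blinded rating as the efficacy version, and the choice of rating for analysis could be left to an analysis plan. This is a fair reading and may be what was meant. But the protocol never says that two ratings exist. Whether appearance is assessed at three visits, and by whom, is a matter of data collection on which the protocol itself has to be consistent.

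Several stronger conclusions that a reader might draw are not supported:

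- *Three visits of endpoint data are lost.* Photographs are taken at all three visits under both schedule and text, and the scale is completed from photographs. Blinded ratings can still be made later.
- *The 3-year result is compromised.* The schedule marks Day 0, 1 year and 3 years. Only the course between years 1 and 3 is affected.
- *Raters change between visits and break the time course.* The text lists the investigator at every follow-up visit, and the form names a blinded physician without limiting the visits. Neither source switches raters.
- *A primary measure is affected.* Primary measure (b) concerns severity, and overall clinical appearance is listed separately. The appearance scale is the only photograph-rating form described, so the two may overlap, but the protocol does not equate them.

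**Conclusion.** The inconsistency is real and its effect is limited. Appearance is rated at 7 of 10 post-treatment visits under the schedule and 10 of 10 under the text, a difference of up to 90 subject-visits. At all 10 visits the rater whose score counts as the endpoint is unstated. The consequences are an undefined time course between years 1 and 3 and a risk, not a plan, that an unblinded score is used for an endpoint outside the primary measures.

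The figure of 90 assumes that all 30 subjects are treated and attend every visit; dropout lowers it. The view that blinded ratings remain recoverable assumes that follow-up photographs cover the control as well as the treated sites. The baseline text says so, while the follow-up lists say only photography.

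**What to change.** 1. State that the blinded photograph rating is the endpoint version of overall clinical appearance.
2. Mark it in the schedule at every visit with photographs, including 1.5, 2 and 2.5 years.
3. In the visit text, either remove the investigator's appearance item or keep it, labelled as unblinded and supportive.
4. List the scale, or its photograph reading, in the Day 0 text so that it agrees with the schedule.
5. Give the blinded reader coded site labels. The form as printed names the treatment of each site, so naming a blinded rater does not by itself secure blinding.

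The cost is a text edit and more reading. The schedule now implies 8 photograph sets per subject (Day 0 plus 7), or 8 × 30 = 240. The change gives 11 per subject (Day 0 plus 10), or 11 × 30 = 330. The difference is 330 − 240 = 90 sets at most for the existing blinded reader. No visit or photograph is added.
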